1.6 Data Safety Monitoring Committee

(ICH/E6 6.1.7; SPIRIT 5a-d)

ICH: Name(s) and address(es) of the clinical laboratory(ies) and other medical and/or technical department(s) and/or institutions involved in the trial.

N/A

1.7 Any other relevant Committee, Person, Organisation, Institution

(ICH/E6 6.1.7; SPIRIT 5a-d)

ICH: Name(s) and address(es) of the clinical laboratory(ies) and other medical and/or technical department(s) and/or institutions involved in the trial.

N/A

2. ETHICAL AND REGULATORY ASPECTS

(ICH/E6 6.12; AGEK 11; SPIRIT #24, 5)

ICH: Description of ethical considerations relating to the trial.

The decision of the CEC authority concerning the conduct of the study will be made in writing to the Sponsor before commencement of this study. The clinical study will only begin once approval from all required authorities has been received. Any additional requirements imposed by the authorities will be implemented.

2.1 Study registration

(ClinO, Art. 1d, 64; SPIRIT #2a-b)

This study will be registered at clinicaltrials.gov as a primary register and, additionally, it will be registered in the Swiss Federal Complementary Database as soon as the ethics application is approved by the CEC.

2.2 Categorisation of study

(ClinO, Art. 19, 20, App 3, 1.1)

The study is a clinical trial with MD risk category I (wireless accessories (transmitters and receivers)) and risk category IIA (hearing aids, acoustic couplings (receivers, tubes, earpieces) and fitting software). All medical devices in this trial are CE-labelled and the application is done according to the specialized information.

2.3 Competent Ethics Committee (CEC)

(ClinO, Art 24-29; SPIRIT #24)

The responsible investigator ensures that approval from an appropriately constituted CEC is sought for the clinical study.

Reporting duties and allowed time frame have to be abided concerning all changes in the research activity and all unanticipated problems involving risks to humans, including in case of planned or premature study end and the final report. No changes are made to the protocol without prior Sponsor and CEC approval, except where necessary to eliminate apparent immediate hazards to study participants.

Premature study end or interruption of the study is reported within 15 days. The regular end of the study is reported to the CEC within 90 days, the final study report will be submitted within one year after study end. Amendments are reported according to chapter 2.10.

2.4 Competent Authorities (CA)

(ClinO, Art. 23, 27, 30-39, 42, 43, 46-48, 57; SPIRIT #24)

There is no need for a CA approval or other local requirements because this study is of risk category according to LHR A.

(ClinO, Art. 5; AGEK 11; ICH E6 6.12, 6.2.5)

ICH: A statement that the trial will be conducted in compliance with the protocol, GCP and the applicable regulatory requirement(s).

The study will be carried out in accordance to the protocol and with principles enunciated in the current version of the Declaration of Helsinki, the guidelines of Good Clinical Practice (GCP) issued by ICH, in case of medical device: the European Directive on medical devices 93/42/EEC and the ISO Norm 14155 and ISO 14971, the Swiss Law and Swiss regulatory authority's requirements. The CEC and regulatory authorities will receive annual safety and interim reports and be informed about study stop/end in agreement with local requirements.

2.5 Declaration of interest

(ClinO, Art. 3b; SPIRIT #28)

In accordance to ISO 14155 and KlinV, Art. 3b scientific integrity will be preserved. Therefore, any potential conflicts of interest, including financial, that interfere with the conduct of this clinical investigation or interpretation of the according results could be disclosed.

2.6 Patient Information and Informed Consent

(ClinO, Art. 7-9, Art. 15-17, Appendix 3, 1.4, 2.4, 3.4, 4.3, Appendix 4, 3.6; AGEK submission checklist item 5; SPIRIT #26, 32)

The investigators will explain to each participant the nature of the study, its purpose, the procedures involved, the expected duration, the potential risks and benefits and any discomfort it may entail. Each participant will be informed that the participation in the study is voluntary and that he may withdraw from the study at any time and that withdrawal of consent will not lead to consequences for the participant. The participant must be informed that his medical records may be examined by authorized individuals.

All participants for the study will be provided a participant information sheet and a consent form describing the study and providing sufficient information for participant to make an informed decision about their participation in the study. The participants will be given enough time (minimum time frame for this study: 1 week) for their participation decision. The patient information sheet and the consent form will be submitted to the CEC to be reviewed and approved.

The formal consent of a participant, using the approved consent form, must be obtained before the participant is submitted to any study procedure. The participant should read and consider the statement before signing and dating the informed consent form, and should be given a copy of the signed document. The consent form must also be signed and dated by the investigator (or his designee) and it will be retained as part of the study records.

2.7 Participant privacy and confidentiality

(ClinO, Art. 18; ICH/E6 6.10; AGEK 12.2, SPIRIT #27)

ICH: The sponsor should ensure that it is specified in the protocol or other written agreement that the investigator(s)/institution(s) will permit trial-related monitoring, audits, IRB/IEC review, and regulatory inspection(s), providing direct access to source data/documents.

The investigator affirms and upholds the principle of the participant's right to privacy and that they shall comply with applicable privacy laws. Especially, anonymity of the participants shall be guaranteed when presenting the data at scientific meetings or publishing them in scientific journals.

Individual subject audiological information obtained as a result of this study is considered confidential and disclosure to third parties is prohibited. Subject confidentiality will be further ensured by utilising subject identification code numbers to correspond to measurement data in the computer files.

For data verification purposes, authorised representatives of the Sponsor, a competent authority (e.g.

Swissmedic), or an ethics committee may require direct access to parts of the measurement records relevant to the study, including participants' audiological history.

2.8 Early termination of the study

(ClinO Art. 47; ICH/E6 6.4.6; SPIRIT #21b)

ICH: A description of the "stopping rules" or "discontinuation criteria" for individual participants, parts of trial and entire trial.

The Sponsor or the Principle Investigator may terminate the study prematurely according to certain circumstances, for example:

- ethical concerns,
- insufficient participant recruitment,
- when the safety of the participants is doubtful or at risk, respectively,
- alterations in accepted clinical practice that make the continuation of a clinical trial unwise,
- early evidence of benefit or harm of the experimental intervention

2.9 Protocol amendments

(ClinO, Art. 29, 34, 55; SPIRIT #25)

Every person who is involved in the study performance is able to draft an amendment. All amendments have to be reviewed and signed by the Principle Investigator of the main study site before they get forwarded to the responsible approval institution.

Substantial amendments are only implemented after approval of the CEC.

Under emergency circumstances, deviations from the protocol to protect the rights, safety and well-being of human subjects may proceed without prior approval of the sponsor and the CEC. Such deviations shall be documented and reported to the sponsor and the CEC as soon as possible.

All non-substantial amendments are communicated if applicable to the CEC within the Annual Safety Report (ASR).

3. BACKGROUND AND RATIONALE

(ICH 6.2; AGEK 3; SPIRIT #6)

This section includes any statements that rely on existing knowledge or published information concerning the study.

3.1 Background and Rationale

(ICH/E6 6.2; AGEK 3.1; SPIRIT #6)

Phonak Hearing Systems pass through different development and study stages. At an early stage, feasibility studies are conducted to investigate new ideas in the form of algorithms, features and functions in an isolated manner. If the benefit of a new idea is proven, its performance is then investigated regarding interdependency between all available algorithms, features and functions running in parallel in a hearing aid (pivotal/pre-validation studies). Consequently, optimizations are undertaken according to the outcomes. Afterwards and prior to product launch, the complete Phonak Hearing Systems undergo a final quality control, amongst others, in terms of clinical trials conducted in a standardized manner by the Phonak Validation Team ("final inspection stage").

For years, the Phonak Validation Team could build extensive knowledge regarding quality control and clinical investigations. During the past three years, a series of studies for the final quality control of the Phonak Hearing Systems has been conducted based on the approved ethics proposal KEK ZH-Nr.2013-0144 "Strukturiertes Post Market Clinical Follow-up (PMCF) zur Qualitätsbeurteilung der ersten Palio3 Feature-, Funktions- und Produktgeneration." [37]. The planned study series within this proposal builds on the experiences of the previous studies in the same way. Please find a brief summary of the study series covered by the past ethics proposal below:

No.	Title	Status	Primary Objective	Secondary Objective	N	Methodology
1	Baseline	completed	Loudness, sound quality, speech intelligibility with individual hearing instrument prescription	Speech intelligibility in noise	22	p/eCRFs, WaKo, Freiburger, OLSA, PPT, sound simulations, REM
2	Palio3 - Active Occlusion Control (AOC)	omitted	x	x	x	x
3	HABS	completed	Acceptance of the automatic program during the individual daily life	Perception of artifacts, efforts on fine tuning, sound balance	66	p/eCRFs, Freiburger, OLSA, PPT, sound simulations, MUSHRA, paired comparison, REM
4	Low Frequency amplification in open fittings	completed	Speech intelligibility	Sound balance	20	p/eCRFs, WaKo, OLSA, PPT, sound simulations, REM
5	Sprachverständlichkeit in schwierigen Hörsituationen	omitted	x	x	x	x
6	System Validation Palio3 CR(M)T	completed	High user's satisfaction with the loudness and sound quality	Increase of hearing instrument acceptance after long-term experience (4wks), efforts on fine tuning, additional benefit from accessories, objective speech intelligibility, frequency of hardware defects	60	p/eCRFs, Freiburger, OLSA, PPT, sound simulations, REM
7a 7b	Palio3 HdO Systeme Palio3 IdO Systeme	running	Equality of the form factors regarding loudness and sound quality perception with individual hearing instrument prescription	Increase of hearing instrument acceptance after long-term experience (4wks), efforts on fine tuning, additional benefit from accessories, objective speech intelligibility, frequency of hardware defects	53	p/eCRFs, Freiburger, OLSA, PPT, sound simulations, REM
8a 8b	Palio3 (Bi)CROS CRT Palio3 (Bi)CROS IdO	running	Objective speech intelligibility in noise	Increase of hearing instrument acceptance after long-term experience (5wks), efforts on fine tuning, subjective speech intelligibility	32	p/eCRFs, Freiburger, OLSA, PPT, sound simulations, REM
9	Palio3 Power	To be planned	Equality or improved performance of the new power devices compared to appropriate predecessor regarding loudness and sound quality perception with individually calculated prescription	New system works reliable and no malfunctions occur	40	p/eCRFs, Freiburger, OLSA, PPT, sound simulations, REM

10	Benchmark	omitted	x	x	x	x
----	-----------	---------	---	---	---	---

Table 2: Overview of study series: KEK ZH-Nr.2013-0144.

3.2 Investigational Product (treatment, device) and Indication

(ICH/E6 6.2.1; AGEK 2; SPIRIT #6)

ICH: Name and description of the investigational product(s).

All hearing systems (Phonak and competitor) are CE-labelled MD of risk category I and IIA. All MDs (hearing instruments, earpieces and wireless accessories) are bearing product names and unique serial numbers for an unambiguous assignment and retracing of the product to the subject. The hearing systems will be set and fine-tuned to the individual hearing loss and needs of the subject by using the corresponding fitting software (table 3) in accordance to the specialised information whereof the latest version can always be printed out of the Phonak Fitting Software, Target.

Manufacturer	Fitting Software
Phonak	Target
Oticon	Genie
Widex	Compass
Siemens	Connexx
Starkey	Inspire
Audio Service	Connexx

Table 3: Overview of hearing instrument companies with their appropriate fitting software.

Hearing Instruments:

In general, the hearing instruments themselves can be separated in different form factors: In-The-Ear (ITE), Receiver In Canal (RIC) and Behind-The-Ear (BTE) including different acoustic couplings depending on the hearing loss and on the anatomical conditions of the hearing aid user, see figures 1-4 below (source: http://www.phonak.com/ch/b2c/de/products/hearing_instruments/styles-10.html and https://www.phonakpro.com/content/dam/phonak/gc_us/Documents/Product/RIC/RIC%20Acoustic_Coupling_Guide_028-0555-03.pdf, status: 07.05.2015).

[figure not shown]

Figure 1: In-The-Ear (ITE)

Figure 2: Receiver In Canal (RIC)

[figure not shown]

Figure 3: Behind-The-Ear (BTE)

[figure not shown]

Figure 4: Different acoustic couplings offered by Phonak (receiver and coupling options/earpieces).

Earpieces:

Together with a BTE or RIC, the earpiece is a system which is also of medical device risk category IIA. Without the merge of the earpiece and hearing aid the earpiece has no medical harness.

Wireless Accessories:

The Phonak Wireless Accessories comprise various solutions to simplify the volume adjustment as well as the program switching in a hearing aid but also to enhance speech intelligibility in noisy environments, in making phone calls or in bridging distances between a talker and the hearing aid user like in class/conferences/lectures. The signal processing is based on frequency modulation (FM) technology, digital modulation (DM) technology, bluetooth (direct streaming, e.g. from the cell phone to the hearing instrument) and/or a specific signal processing algorithm developed by Phonak itself, the HIBAN (hearing instrument body area network), respectively. The subsequent current Phonak Wireless Accessory solutions are MD of risk class I: Phonak ComPilot, Phonak PilotOne, PhonakComPilot Air, RemoteControl App, Roger Pen, Roger Clip-On Mic, Roger for Education and their corresponding receivers. Phonak products which are no MD but which are also investigated are: Phonak DECT, Phonak EasyCall, Phonak RemoteMic and Phonak TVLink (figure 5, source: <http://www.phonak.com/com/b2c/en/products/wireless-accessories.html>, status: 18.05.2015). They also have a unique serial number for an unambiguous assignment and retracing of the product to the subject. The intended purpose is also according to the instruction manual.

Figure 5: Some examples of Phonak Wireless Accessories.

3.3 Preclinical Evidence

(ICH/E6 6.2.2; SPIRIT #6a)

ICH: A summary of findings from nonclinical studies that potentially have clinical significance

For MD this entry is only applicable if needed for pre-marketed / marketed devices needing Swissmedic notification (Guidance on the biological evaluation of medical devices is given in ISO 10993). Therefore, this entry is not applicable for this study.

3.4 Clinical Evidence to Date

(ICH/E6 6.2.2; SPIRIT #6a)

ICH: A summary of findings from ... and from clinical trials that are relevant to the trial.

There is no available clinical research data to date on the investigational product.

3.5 Dose Rationale / Medical Device: Rationale for the intended purpose in study (pre-market MD)

(ICH/E6 6.2.4; SPIRIT #6a)

ICH: Description of and justification for the route of administration, dosage, dosage regimen, and treatment period(s).

The hearing instruments will be set and fine-tuned to the individual hearing loss and needs of the subject in accordance to established audiological test methods and according to the best knowledge and conscience of trained staff. The Sonova Validation Team is experienced in hearing instrument fitting for more than 15 years.

3.6 Explanation for choice of comparator (or placebo)

(AGEK 11.3; SPIRIT #6b)

In this study, hearing instruments of previous Phonak generations or competitors are compared with the latest Phonak hearing aid technology to evaluate the current overall product status.

3.7 Risks / Benefits

(ClinO, Appendix 4, 3.5; Art 25d2; ICH/E6 6.2.3; AGEK 11.1; SPIRIT #6a; MD: ISO 14155 Annex A & ISO 14971)

ICH: Summary of the known and potential risks and benefits, if any, to human subjects.

There are five known risks:

1. Infections can be caused by injuries of the ear canal which can occur by the placement of the acoustic coupling (e. g. receiver, earpiece) to the outer ear canal or by the placement of an ITE device. Therefore, the ear canal will be thoroughly checked and assessed during the study.
2. Pressure points can be caused by the hearing aid or the acoustic coupling. In case of pressure points, the hearing aid should not be worn until it healed up. The cause of the pressure point would then be investigated.
3. Tinnitus can be cause by wearing of the hearing aids. An existing tinnitus can be temporarily amplified. If the tinnitus doesn't improve after several days of not wearing the hearing aid, an assessment with an independent doctor (ENT) is necessary.
4. A headache can occur, especially for new hearing aid users. If a headache appears, the subject is instructed to interrupt the hearing aid use until the audiologist applies a new fitting (e.g. reduced gain level) to acclimatize the subject to the devices.
5. The hearing aid can reach a high maximum power output (MPO). The MPO will be set accordingly to clinical expertise at a level that no injuries can occur.

3.8 Justification of choice of study population

(ClinO, Art 25d4, Art. 15-17; ICH/E6 6.2.6; AGEK 11.2)

ICH: Description of the population to be studied.

In this study, adult hearing impaired persons with different degrees of hearing loss will participate. The sound processing in the inner ear significantly differs between normal hearing and hearing impaired persons and, furthermore, is dependent on the degree of the hearing loss. For this reason, the sound quality and the benefit of new hearing systems, which can be individually fitted to a hearing loss, can only be reliably evaluated by appropriate hearing impaired persons.

In addition, both persons with hearing aid experience (i.e. owning hearing aids) and without this experience can participate. Hearing impaired persons are categorized as a vulnerable population since in both cases (with and without hearing aid experience), they might expect a benefit from the study participation in the form of, e.g. a cheaper acquisition of the newest hearing system technology directly from the Sonova AG which is not possible.

4. STUDY OBJECTIVES

(ICH/E6 6.3; AGEK 3; SPIRIT #7)

ICH: A detailed description of the objectives and the purpose of the trial.

4.1 Overall Objective

A successive methodical evaluation of new CE-Labelled Phonak Hearing Systems (hearing instruments, acoustic couplings, wireless accessories and fitting software) on hard of hearing participants will be conducted to grant quality control prior to product launch.

4.2 Primary Objective

The study seeks primarily to grant zero-defect overall performance of the new Phonak Hearing Systems.

4.3 Secondary Objectives

Secondary objectives are to assess efficacy of the new Phonak Hearing Systems compared to previously outstanding Phonak Hearing Systems and to competitor devices.

4.4 Safety Objectives

With regard to a continuous improvement of the various algorithms running in parallel in a hearing systems, the study aims to assess long-term safety of the Phonak Hearing Systems.

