HRA	Federal Act on Research involving Human Beings
IMP	Investigational Medicinal Product
IIT	Investigator-initiated Trial
ISO	International Organisation for Standardisation
ITT	Intention to treat
KlinV	Verordnung über klinische Versuche in der Humanforschung (in English: ClinO, in French OClin)
LPTth	Loi sur les produits thérapeutiques
LRH	Loi fédérale relative à la recherche sur l'être humain
MD	Medical Device
MUSHRA	Multi-Stimulus Test with Hidden Reference and Anchor
N/A	Not Applicable
OClin	Ordonnance sur les essais cliniques dans le cadre de la recherche sur l'être humain (in German : KlinV, in English : ClinO)

OLSA	Oldenburger Satztest
PI	Principal Investigator
PL	Project Leader
PM	Product Manager
PPT	Phoneme Perception Test
REM	Real-Ear Measurement
RIC	Receiver-In-The-Channel device
SDV	Source Data Verification
SNR	Signal-to-Noise Ratio
SOP	Standard Operating Procedure
SPC	Summary of product characteristics
SPL	Sound Pressure Level
SRT	Speech Reception Threshold
SUSAR	Suspected Unexpected Serious Adverse Reaction
TEN test	Threshold-Equalizing-Noise test
TMF	Trial Master File
UAT	User Acceptance Test
UCL	UnComfortable Level
WaKo	Einsilber-Reimtest nach von Wallenberg und Kollmeier

STUDY SCHEDULE

(AGEK 4.2; SPIRIT #13; ICH E6 6.4.2)

Studies are organized in, a potential pre-study if needed, and the main study itself. A pre-study would be organized as follows:

Study Period	Screening	Pre-study appointments		Follow-up (final appointment)
Visit Number	1	2	3	4
Time [hrs]	1.5	2	2	2
Audiological History	x			
Physical Examination of Ear and Ear Canal	x	x	x	x
Audiogram	x			x
Tinnitus Matching	x			x
Check In- /Exclusion Criteria	x			
Decision Subject Participation	x			
Subject Information and Informed Consent	x			
Encoded Subject ID	x			
eCRF Screening	x			
eCRF Audiometry	x			x
Randomisation	x			
Hearing System Fitting	x	x	x	
Objective and Subjective Measurements		x	x	(x)
eCRF Objective and Subjective Measurements		x	x	(x)
Introduction to Handling		x	x	
Scheduling Next Visit		x	x	
eCRF Final Appointment				x
Capture of Adverse Events and Device Deficiencies	x	x	x	x

Table 1a: Pre-study: N = max 5

Study Period	Screening	Study appointments										Final Appointment
		2	3	4	5	6	7	8	9	10	11	
Visit Number	1	2	3	4	5	6	7	8	9	10	11	12
Time [hrs]	1.5	2	2	2	2	2	2	2	2	2	2	2
Audiological History	x											
Physical Examination of Ear and Ear Canal	x	x	x	x	x	x	x	x	x	x	x	
Audiogram	x											x
Tinnitus Matching	x											x

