5.3 Other Outcomes of Interest

Other outcomes of interest are side-effects.

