5.4 Safety Outcomes

N/A

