In total, a maximum of 210 adult subjects will participate per year. If necessary, there will be a pre-study with a maximum of five internal (normal hearing or hearing impaired) subjects before the main study to prove the actual study design. A pre-study will be considered if there are adjustments away from the normal audiological standard regarding the method, setup, subject group etc. If a pre-study is necessary will be decided by the principal investigator. Then, according to experience, 6 clinical trials (main studies) with a maximum of 30 subjects per study each of two months duration, are conducted for a quality control of the Phonak Hearing Systems. Typically, each participant gets a series of weekly appointments of 1.5 to 2 hours (lab trials), respectively, including the fitting procedure of the hearing system as well as the objective tests. Between the weekly appointments, the home trials take place so that the subjects can test the devices in their daily life in accordance to some questionnaires either pCRF or eCRF. In dependence on the form factor of an investigational product, which provide different gain levels, participants with appropriate hearing losses ranging from mild, moderate, severe to profound need to be recruited. Testing takes place in one of the three double-walled sound-attenuating booths (Validation Room 1, 2 and 3, see section 9.2.1).

Despite of the well-defined study protocol, some limitations of the study design are inherent. For example, it is not possible to blind the investigational product during the home trial. Especially the housing/naming of competitor devices are revealing their identity. During the lab trials, the participants are fully blinded. An additional limitation of the study design are software updates during the study for both the fitting software and the hearing systems. As soon as quality problems occur, such as acoustic feedback problems or artefacts, for example, a device deficiency form is filled in and the devices get revised leading to different firmware versions across the study which need to be considered during the data analysis.

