9.2.1 Assessment of primary outcome

ICH: Methods and timing for assessing, recording, and analysing of efficacy & safety parameters.

Procedure: After a successful screening as described in section 7.2, the data serving as primary outcomes are collected in a series of appointments lasting 1.5 to 2 hours each for the lab trials and one week for the home trials taking place between the lab trial appointments. The subjective and objective measurements that are applied to grant zero-defect overall performance of the new Phonak Hearing Systems regarding technical stability, audiological performance and handling are listed in section section 5.1. The general procedure of a lab trial can be described in a flow chart as follows:

[figure not shown]

Figure 6: Schematic procedure of a lab trial.

Testing takes place in one of the three double-walled sound-attenuating booths (Validation Room 1, 2 and 3). Participants are tested individually. All of them comfortably sit on a chair in the middle of the room and are consistently instructed what their task is both written in terms of standardized instructions and verbally to ensure that the task is understood. Then, stimuli (speech: words, numbers or sentences in quiet or in a specific background noise, also music or sound simulations, like an in car situation, in a cafeteria or in a reverberated room) are presented with a computer and loudspeakers of a number and of a defined arrangement according to the test method used, see figures 7 and 8. In case of a closed-set speech test, the participant are instructed to choose an answer on a touch screen. In case of an open-set task, the participant is asked to verbally repeat the things understood.

Instead of loudspeaker presentations also headphone presentations simulating hearing aids (single features or functions) as well as sound situations by pre-recorded sound files can be presented to the participant. The advantage is a highly controlled listening situation and a simple possibility to quickly switch between different hearing aids (or settings) in case of a paired comparison or a MUSHRA task which use subjective rating on a rating scales to evaluate different dimensions.

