11.4.5 Safety analysis

The safety analysis will be permanently done during the study by the PI.

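### Section 4.4 promises long-term safety, but scheduled follow-up is about two to two and a half months and no safety outcome is defined in 5.4

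*Combined protocol and SAP*

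**What the plan says.** Section 4.4 states the safety objective: "the study aims to assess long-term safety of the Phonak Hearing Systems".

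The sections that should turn this into something measurable are thin. Under "5.4 Safety Outcomes" the only entry is N/A. Section 5.3 says "Other outcomes of interest are side-effects", with no variable, time point or metric. Section 11.4.5 says "The safety analysis will be permanently done during the study by the PI", with no method or summary measure.

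On duration, section 6.1 describes the main studies as "each of two months duration" and says that, typically, "each participant gets a series of weekly appointments of 1.5 to 2 hours (lab trials". Section 9.2.1 gives "one week for the home trials taking place between the lab trial appointments". The header of Table 1b in the Study Schedule runs "Visit Number 1 2 3 4 5 6 7 8 9 10 11 12", where visit 1 is screening and visit 12 the final appointment. Section 8.9 has all study devices returned at that final appointment.

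Safety-relevant data are collected. Table 1b schedules adverse events and device deficiencies at every visit, and audiogram and tinnitus matching at screening and final visit. Sections 7.2, 9.3.1 and 9.3.4 limit tinnitus matching to participants who have tinnitus.

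**The concern.** An objective about long-term safety needs participants to be observed for a long time, and needs a variable that is summarised over that time. The plan supplies neither. The scheduled observation is a matter of weeks, and the section reserved for safety outcomes is marked as not applicable.

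The practical risk lies in what is said afterwards. Section 13 allows study results to support product claims in brochures for professionals and end users. A protocol that names long-term safety as an aim, with no definition of how it is judged, leaves room for a statement that a few weeks of data in at most 30 people cannot carry. Conversely, the short-term data that do exist, including hearing thresholds before and after, have no planned group summary in the sections supplied.

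**Working it through.** **Inputs.** Stated duration of a main study: two months (6.1). Visits: 12 (Table 1b). Interval: one week, described as typical (6.1, 9.2.1). Maximum size of a main study: 30 (6.1). Status update after an adverse event: for example after one to two weeks (10.3.2). Length of the series: ten years (6.1).

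**Step 1: reproduce the stated duration.** Two months = 2 × 365.25/12/7 = 8.7 weeks. The study appointments alone (visits 2 to 11) span 9 intervals = 9 weeks = 2.07 months, close to the stated figure.

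**Step 2: follow-up per participant.**
- Screening to final visit: 12 − 1 = 11 intervals × 7 = 77 days = 11 weeks = 2.5 months.
- Visit 2 to final visit: 12 − 2 = 10 weeks. This may be closer to actual wearing time. Table 1b marks fitting at visit 1, but introduction to handling starts at visit 2 and the screening list in 9.3.1 includes no fitting.
- With an event-triggered status update after the final visit: 11 + 1 = 12 to 11 + 2 = 13 weeks.

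**Step 3: time per device.** The plan does not state period lengths. Assuming equal periods in a cross-over, and using 8.7 to 11 weeks in total:
- two devices: 8.7/2 = 4.3 to 11/2 = 5.5 weeks each;
- three devices: 8.7/3 = 2.9 to 11/3 = 3.7 weeks each.

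In a parallel-group study, which the synopsis and 11.2 also allow, a participant might keep one device for the whole time. The ceiling is then again about 11 weeks.

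**Step 4: what zero events would show.** The one-sided 95% upper limit with 0 events in n participants is 1 − 0.05^(1/n).

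| n | Source of n | Upper limit |
|---|---|---|
| 10 | smaller parallel group (11.2) | 25.9% |
| 15 | larger parallel group (11.2) | 18.1% |
| 20 | typical past study (11.2) | 13.9% |
| 30 | maximum per main study (6.1) | 9.5% |
| 180 | 6 × 30, one year pooled | 1.65% |

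The last row assumes that all six main studies of a year are pooled as if they tested one product; the plan describes no such pooling. Every row concerns risk over weeks. A larger n narrows the limit but does not lengthen the observation.

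**Step 5: is there a long-term source elsewhere?** The ten years in 6.1 are the life of the series. Section 6.1 also says that firmware may change within a study. Section 6.2 requires a break of at least six months before a participant enters another study. No section supplied links a participant's records across studies or plans a cumulative safety summary. The annual safety reports in 2.4 come with no long-term outcome.

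**The case against.** **The series is long-term.** The sentence in 4.4 opens with continuous improvement of the algorithms, and 6.1 speaks of ensuring performance across ten years. So long-term may refer to the product line, not to a person. This is the best defence of the wording. It still needs a variable and a way of combining studies of changing devices, and neither is described.

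**The sponsor uses the term for weeks.** Table 2 in section 3.1 calls 4 and 5 weeks long-term experience. That concerns acceptance of hearing instruments in the previous series. Section 4.4 does not define the term. If weeks are meant, 4.4 should say so, which is the change proposed.

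**Safety is handled.** Much of this stands. A reader might infer from N/A in 5.4 that no safety data are collected, that nothing can follow the final visit, or that the audiogram and tinnitus data have no safety role. The documents support none of these. Adverse events and device deficiencies are captured at every visit, and 5.3 names side-effects. Sections 9.2.5, 9.3.4 and 10.3.2 provide additional appointments when an event or a stronger tinnitus is found. Section 9.3.4 compares the final tinnitus match with screening, and 9.2.5 uses an audiogram and ear check at withdrawal to look for harm. These are safeguards for the individual. They are neither long follow-up nor a group-level analysis.

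**Section 9.2.4 may define the outcomes.** The contents list names a section on assessment of safety outcomes that is not in the text available here. Its absence is not held against the plan. It could add measurements, but would be unlikely to lengthen the visit schedule, and the N/A in 5.4 would still need to be reconciled with it.

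**Weight.** Safety is neither the primary nor the secondary objective, the devices are CE-labelled, and 11.1 says that no specific hypothesis is tested. This limits the seriousness of the point but does not remove the contradiction.

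**Conclusion.** The objective in 4.4 cannot be met by the design described. Scheduled follow-up is about 8.7 weeks by the stated duration and 11 weeks by the visit table; the event-triggered status update that 10.3.2 gives as an example would take it to 12 or 13. No outcome or summary measure is tied to long-term safety in 5.3, 5.4 or 11.4.5.

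The data can support a short-term safety statement, and a modest one: an upper limit of 9.5% with no event in 30 participants.

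The 11 weeks rests on weekly visits, which the plan calls typical and does not fix. The 9.5% applies to one main study at its maximum size. It would be inferring too much to say that every participant's time is split between devices, because parallel groups are allowed. The conclusion about long-term safety depends on none of these details. The point calls for correction before results are reported. It is not a reason to doubt the safety procedures themselves.

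**What to change.** 1. **Section 4.4:** replace 'long-term safety' with 'safety over the participant's study period'.
2. **Sections 5.3 and 5.4:** reconcile them by replacing N/A with outcomes from data already scheduled:
   - the proportion of participants with any adverse event, and the proportion with any device deficiency, each by the device in use at onset;
   - the change in pure-tone threshold from screening to final visit;
   - in participants with tinnitus only, the change in tinnitus match from screening to final visit.
3. **Section 11.4.5:** report the proportions with exact 95% confidence intervals. Report the changes as mean or median with a 95% confidence interval and the number of participants contributing, since exact binomial intervals do not apply to them.
4. **Section 9.2.4:** check that it agrees with the new 5.4.

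No new visit or measurement is needed. The sponsor gives up the long-term wording and takes on a short descriptive analysis and a protocol amendment; under 2.9, a substantial amendment must be approved by the ethics committee before it is implemented. Keeping the long-term wording would cost more, because follow-up and outcomes to match it would have to be added.
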